Regulation of gut microbiota through dietary interventions (e.g., probiotic intake) may be beneficial in reducing inflammation [hs-CRP and Ceruloplasmin (Cp)] and oxidative stress [Glutathione (GSH) and Malondialdehyde (MDA)], as well as regulating glucose and lipid metabolism in T2DM. The aim of this study was to investigate the effects of probiotics on glucose and lipid metabolism, inflammation and antioxidant system in patients with T2DM.

Methods

Trial design

This was a single center, prospective controlled study conducted at the Internal Medicine Outpatient Clinic of Ege University Faculty of Medicine between July 2020 and June 2023. The study included a screening visit, a baseline visit (D0) and one follow-up visit during a 60-days supplementation period. The primary outcomes of the study were defined as the effects of the intervention on inflammatory markers, specifically focusing on a significant decrease in hsCRP and Cp levels, and oxidative stress markers, including a significant reduction in MDA levels and a significant increase in reduced GSH levels. Secondary outcomes included assessing the metabolic and lipid profile changes, which specifically targeted a significant decrease in Fasting Blood Glucose (FBG), Postprandial Blood Glucose (PPBG), and Glycated Hemoglobin (HbA1c), alongside a reduction in LDL-C and Triglyceride (TG) levels, and an increase in High-Density Lipoprotein Cholesterol (HDL-C) levels.

Trial participants

Power analysis was performed and the sample size was calculated as 79 with a statistical power of 80% and an effect size of 0.35. Since two groups were to be studied, 80 patients were planned to participate in the study to equalize the number of participants.

This study included adults aged 35-65 years who were diagnosed with T2DM according to American Diabetes Association guidelines, who volunteered to participate in this study. Exclusion criteria were as follows: Use of any systemic antibiotics, multivitamins, minerals, herbal medicines, prebiotic, probiotic and postbiotic supplements in the last 3-6 months, any inflammatory bowel disease, severe renal dysfunction or hepatic dysfunction, immunodeficiency diseases, acute infection, rheumatoid arthritis, cancer history, history of alcohol abuse or drug dependence, pregnant or lactating women. Dietary habits, physical activity, and glucose-lowering therapy of the participants were not intervened during the study.

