The EAT-26 was developed for Garner et al.[24]. The test consists of 26 items, and the total score is between 0-53. A score of 20 and above is defined as “abnormal eating behavior” and a score less than 20 is defined as “normal eating behavior”. The Turkish validity and reliability study was conducted by Erguney-Okumus and Sertel-Berk [25].

Biochemical measurements

Fasting blood samples were collected from the participants at baseline and week 12, following overnight fasting and after 2 hours of satiety. FBG, PPBG, HbA1c, Total-C, LDL-C, HDL-C, TG and hs-CRP were measured using an autoanalyzer. Serum MDA levels were determined by the thiobarbituric acid method [26], GSH levels by enzymatic recycling method [27] and Cp levels by colorimetric method [27] using a microplate reader.

References

4. Choi SH, Chae A, Miller E, Messig M, Ntanios F, DeMaria AN, et al. Relationship Between Biomarkers of Oxidized Low-Density Lipoprotein, Statin Therapy, Quantitative Coronary

Angiography, and Atheroma Volume. *J Am Coll Cardiol.* 2008;52:24–32. <https://doi.org/10.1016/j.jacc.2008.02.066>.

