OFFICIAL TITLE:

*THE EFFECTS OF PROBIOTICS ON
METABOLIC BIOMARKERS,
INFLAMMATION, AND THE
ANTIOXIDANT SYSTEM IN PATIENTS
WITH TYPE 2 DIABETES MELLITUS*

Date: 17.04.2018

Statistical Analysis Plan (SAP)

Statistical analysis was performed using SPSS 25.0 statistical package program. Data from all patients who completed the study were included in the statistical analysis. For descriptive findings, categorical variables were presented as numbers and percentages, and continuous variables were presented as mean, standard deviation, minimum value and maximum value. Kolmogorov-Smirnov normality tests were used to determine whether the data showed normal distribution. Pearson chi-square test was used to analyse categorical variables. Parametric tests (t test in independent groups, t test in dependent groups) were used in the analysis of normally distributed data, and non-parametric tests (Mann-Whitney U test, Wilcoxon Signed Rank Test) were used in the analysis of non-normally distributed data. Statistical significance level was accepted as $p<0.05$.

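### Four unranked primary markers are each tested at p<0.05 with no success rule, adjustment or named confirmatory test; if any one marker counts, a false favourable claim has a 6.5% to 9.6% chance instead of 2.5%

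*SAP*

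**What the plan says.** The protocol (Methods, Trial design) sets out the primary outcomes in two pairs. The inflammatory pair is described as "specifically focusing on a significant decrease in hsCRP and Cp levels". The oxidative-stress pair is described as "including a significant reduction in MDA levels and a significant increase in reduced GSH levels". That makes four markers, each with a direction, and statistical significance is part of how each outcome is defined. None is placed above the others.

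The SAP is a single paragraph. It sets one threshold for everything: "Statistical significance level was accepted as $p<0.05". On method it says "Parametric tests (t test in independent groups, t test in dependent groups) were used in the analysis of normally distributed data", with the Mann-Whitney and Wilcoxon signed-rank tests as the non-normal counterparts. It does not say which of these tests decides the primary question, whether the between-group test is applied to follow-up values or to change, or whether tests are one- or two-sided. Its analysis set is defined by "Data from all patients who completed the study were included in the statistical analysis".

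On timing, the protocol's Biochemical measurements section says "Fasting blood samples were collected from the participants at baseline and week 12", while Trial design refers to "one follow-up visit during a 60-days supplementation period".

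**The concern.** Because the primary outcomes are worded as significant changes, a positive trial cannot be defined without saying how many markers must be significant and by which test. Both are missing. Someone following the plan as written could test the four markers separately at 5% and present whichever moved the right way as a primary finding.

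The choice of test adds to this. With samples at baseline and follow-up, each marker can yield a between-arm p-value on follow-up values, a between-arm p-value on change, and a within-arm p-value in the probiotic group. A within-arm fall in hs-CRP would fit the protocol's wording literally, yet it is not a comparison with control. At stake is what error rate a reader should attach to any primary claim; the documents do not allow it to be worked out.

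**Working it through.** **No stated figure to reproduce.** The documents give no overall error rate. Their only calculated figure is the sample size (79, 80% power, effect size 0.35), and that statement names no test, outcome or allowance for four primaries. The SAP's t tests do not return it when 0.35 is read as a standardised difference: an independent t test at two-sided 5% needs about 130 per group, a paired t test 67 in all. The calculation below does not depend on it.

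**Inputs from the documents.** Four primary markers with directions; 5% per test; 80 patients in two equal groups, so 40 per arm.

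**Assumptions, none of them in the documents.** Two-sided tests; no true effect; comparable arms; a common correlation ρ between markers once each is oriented to its favourable direction.

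1. *One marker.* Favourable-direction error = 0.05/2 = 2.5%.

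2. *Any of four, independent.* 1 − 0.975⁴ = 1 − 0.9037 = 9.63%.

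3. *Any of four, correlated.* 1 − ∫ φ(u) Φ((1.960 − √ρ·u)/√(1−ρ))⁴ du.

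| ρ | 0 | 0.3 | 0.5 | 0.7 | 0.9 |
|---|---|---|---|---|---|
| Any of four | 9.6% | 8.7% | 7.8% | 6.5% | 4.7% |
| Ratio to 2.5% | 3.9 | 3.5 | 3.1 | 2.6 | 1.9 |

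Simulated t tests with 40 per arm agree within 0.2 points. The ceiling at any correlation is 4 × 2.5% = 10%.

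4. *All four required.* The error cannot exceed 2.5%; with independent markers it is 0.025⁴, effectively zero.

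5. *Outcome form chosen afterwards (follow-up value or change).* With baseline-to-follow-up correlation r, the two between-arm statistics for a marker correlate √((1−r)/2), which is 0.5 at an assumed r = 0.5. Taking the same ρ for both forms, the any-of-four rate is about 17%, 15%, 14% and 11% at ρ = 0, 0.3, 0.5 and 0.7.

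6. *Within-arm change in the probiotic group also allowed.* This depends on drift over time, not only on the treatment effect.
   - With no drift, the rate at ρ = 0 is about 16% (between-arm change or within-arm change, simulated t tests).
   - With an assumed favourable drift of 0.1 SD of the change score in both arms, and still no treatment effect, the within-arm statistic shifts by 0.1 × √40 = 0.63. Each within-arm test is then favourable with probability about 1 − Φ(1.960 − 0.632) = 0.092. The four alone give 1 − 0.908⁴ ≈ 32%, and with the between-arm tests added about 34% (simulation).

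7. *Under Holm.* The first step uses 0.05/4 = 0.0125 two-sided, or 0.00625 in the favourable direction. With one fixed form, any-of-four is 1 − 0.99375⁴ = 2.5% at ρ = 0 and 1.8% at ρ = 0.7. If the form is left open it is about 4.5% to 4.7% at ρ = 0 (r = 0.3 to 0.7), so Holm alone is not enough.

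8. *Price of Holm (noncentral t, 80% power, 40 per arm).* The detectable difference is 0.634 SD of the analysed outcome at 0.05 and 0.762 SD at 0.0125. With an assumed 36 completers per arm it is 0.670 and 0.805. If 0.35 is read as a two-group standardised difference, which the protocol does not say, single-marker power is 34% at 0.05 and 17% at the first Holm step. If all four markers had that effect, average power per marker under Holm would be about 19% to 21% at ρ = 0 to 0.7.

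**The case against.** The best reply is that the protocol joins the markers with the word and, so all four might be required; then there is no inflation. That reading is possible, and for that reason 6.5% to 9.6% is a scenario and not the trial's established error rate. A reader might infer that the plan commits itself to an any-one rule, or that its false-positive rate simply is 9.6%. The documents support neither. But a conjunction in a list of outcomes is not a decision rule, and if all four were meant, the SAP still has to say so.

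Second, the SAP never mentions change scores. A reader might infer that it plans three tests per marker. It lists between-group and within-group tests; a between-group test on change is compatible with the text but not named. The figures for an open choice of form show what the wording permits, not what was planned.

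Third, the within-arm rate is not a general estimate. About 16% holds only if markers do not drift over time, and a small favourable drift roughly doubles it.

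Fourth, patients were allocated by alternation and without placebo, which may bias the comparison more than multiplicity does. That stands: all rates here are nominal, and no multiplicity rule corrects such bias. It does not remove the gap.

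Finally, the conduct period was "between July 2020 and June 2023", so a rule written now may come after the analysis. This limits the gain. It does not make unadjusted marker-by-marker claims any safer.

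**Conclusion.** The omission is certain: four unranked primary markers, one 5% threshold, and no success rule, order, adjustment or named confirmatory comparison. Its size is conditional. If any one favourable marker supports a primary claim, with one two-sided between-arm test each, the false favourable rate is 2.6 to 3.9 times that of a single test over assumed marker correlations of 0.7 to 0. It is larger if the outcome form or a within-arm test can be selected afterwards, and there is no inflation if all four markers are required. The point affects how every primary claim is read and is cheap to repair, so it should be fixed.

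**What to change.** First reconcile the follow-up time: Trial design gives 60 days and Biochemical measurements gives week 12 (84 days). Then add to the SAP, for example:

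> The primary test for each of hs-CRP, Cp, MDA and GSH is the between-arm comparison of change from baseline to the follow-up visit, in this one outcome form only. The four p-values are tested with the Holm procedure at an overall two-sided 5%. Efficacy is claimed only for markers that pass in the direction the protocol names. Within-arm, other-form and secondary p-values are exploratory.

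If this is added after the data were analysed, say so and label it post hoc.

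Requiring all four, fixing an order, or naming one primary marker would also close the gap. Holm is suggested because it keeps four separate marker claims and is valid under any correlation. What matters as much is that one form is fixed.

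Cost: one paragraph and no new data. Between-arm tests on change may have to be run, since the SAP does not name them. The SAP's rule for choosing t or rank tests can stay as it is. The statistical price is the loss of power shown in the working: 0.63 to 0.76 SD detectable at the first Holm step with 40 per arm. Change also costs precision relative to follow-up values if the baseline correlation is below 0.5, so the form should be chosen with that in mind and without sight of the results where that is still possible.
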